- A sensitivity analysis adjusting for number of sessions, counselling and adjunctive treatment will be done to verify that the observed differences are not due to imbalance in patient management other than the tested intervention.
- Per protocol analysis.

9. Results analysis

Provisional tables

Table 1 Baseline characteristics for each group. GTR=, TTR=, SD=standard deviation

| Characteristics | Test group (GTR) N=xx | Control group (TTR) N= xx | Group imbalance (p-values) |
|---|-----------------------------|---------------------------------|----------------------------------|
| Females; n (%) | | | |
| Age of infant; n (%) | | | |
| 1–14 days (1–2 weeks) | | | |
| 15–28 days (3–4 weeks) | | | |
| 29–42 days (5–6 weeks) | | | |
| 43–56 days (7–8 weeks) | | | |
| 57–70 days (9–10 weeks) | | | |
| 71–84 days (11–12 weeks) | | | |
| Infant weight in kg; mean (SD) | | | |
| At birth | | | |
| At baseline | | | |
| Excessive crying, distress or unsettlement prior 24h; mean (SD) | | | |
| Age of mother in years; mean (SD) | | | |
| Siblings; n (%) | | | |
| None | | | |
| 1 | | | |
| 2 | | | |
| 3 or more | | | |
| Co-parenting; n (%) | | | |
| Parenting Confidence Score; n (%) | | | |
| Non-clinical range (40 or more) | | | |
| Mild clinical range (36-39) | | | |
| Moderate clinical range (32-35) | | | |
| Severe clinical range (31 or less) | | | |
| Expected response to osteopathic care; n (%) | | | |
| Very well | | | |
| Well | | | |
| Unsure | | | |
| Not very well | | | |
| Not well | | | |
| Missing | | | |

* Significant group imbalance at baseline

Table 2 Effects of treatment on crying time in minutes

| Outcomes | Test group (TTR) N=xx | Control group (GTR) N= xx | Adjusted * between group difference | Unadjusted between group difference |
|----------------------------------|------------------------------|---------------------------------|--|--|
| | Mean (Std.Err) | Mean (Std.Err) | Mean (CI 95%; P-value) | Mean (CI 95%; P-value) |
| Mean daily crying time (minutes) | | | | |
| From day 1 to day 13 | | | | |
| From day 1 to day 6 | | | | |
| From day 7 to day 13 | | | | |
| Daily crying times (minutes) | | | | |
| Day before treatment | | | | |
| Treatment day | | | | |
| Days after treatment | | | | |
| Day 1 | | | | |
| Day 2 | | | | |
| Day 3 | | | | |
| Day 4 | | | | |
| Day 5 | | | | |
| Day 6 | | | | |
| Day 7 | | | | |
| Day 8 | | | | |
| Day 9 | | | | |
| Day 10 | | | | |
| Day 11 | | | | |
| Day 12 | | | | |
| Day 13 | | | | |

* Adjusted for baseline crying time, infant age and prior expectations for osteopathic care

Table 3 Effects of treatment on other outcomes including undesirable events

| Outcomes | Test group (TTR) | Control group (GTR) | Between group difference* |
|--|---------------------|------------------------|------------------------------|
| | N=xx | N= xx | (CI 95%; P-value) |
| Parenting Confidence Score [0–45]; mean (SD) | | | |
| Perceived changes in symptoms; n(%) | | | |
| Completely recovered | | | |
| Much improved | | | |
| Slightly improved | | | |
| No change | | | |
| Slightly worse | | | |
| Much worse | | | |
| Vastly worse | | | |
| Weight changes over 14 days (kg); mean (SD) | | | |
| Satisfaction with received care; n (%) | | | |
| Very satisfied | | | |
| Fairly satisfied | | | |
| Neither satisfied nor dissatisfied | | | |
| Fairly dissatisfied | | | |
| Very dissatisfied | | | |
| Unexpected reactions; n(%) | | | |
| More distress | | | |
| Crying more | | | |
| More unsettled | | | |
| Vomiting more | | | |
| Increased feeding difficulties | | | |
| Increased difficulties sleeping | | | |
| Other | | | |
| Serious adverse events; n(%) | | | |
| Death | | | |
| Hospitalisation | | | |
| Long lasting morbidity | | | |
| Any | | | |

* P-values measured using likelihood ratio test in linear/logistic regression, Mann-Whitney U test for ordinal outcomes, Chi2 for categorical

Table 4 Number of sessions, advice given, additional treatment and effectiveness of blinding

| | Test group (TTR) N=xx | Control group (GTR) N= xx | Between group difference* |
|--|---------------------------|---------------------------------|------------------------------|
| | Mean (SD) | Mean (SD) | (CI 95%; P-value) |
| Number of sessions; mean (SD) | | | |
| Advices; n(%) | | | |
| Managing the baby's sleep pattern | | | |
| Managing the baby's feeding pattern | | | |
| Mother's diet | | | |
| Handling the baby | | | |
| Managing the baby's environment | | | |
| Parenting behaviour | | | |
| Reassure parent/guardian | | | |
| Other | | | |
| Medication and remedies; n(%) | | | |
| Prescribed medication | | | |
| Anti-gas drops | | | |
| Herbal supplements | | | |
| Probiotics | | | |
| Non-cow or anti-allergenic formula milk | | | |
| Omeprazol | | | |
| Other | | | |
| Additional care; n(%) | | | |
| General practitioner | | | |
| Accident and Emergency | | | |
| Unplanned hospital admission | | | |
| Another osteopath | | | |
| Paediatrician | | | |
| Pharmacist | | | |
| Lactation consultation or midwife | | | |
| Other | | | |
| Blinding; n(%) | | | |
| Thinks the baby was in test group (TTR) | | | |
| Thinks the baby was in the control group (GTR) | | | |
| Doesn't know / unsure | | | |

* Adjusted for baseline crying time. P-values measured using likelihood ratio test in liner/logistic regression

Provisional Figures

Figure 1 Flow chart of participant inclusion and follow-up

Figure 2 Average daily crying time during follow-up between groups

Figure 3 Types of manual care received over the treatment period

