| pcs_e9 | fq2.9 | Parenting confidence at 14 days Q9 | Ordinal | 0=No hardly ever; 1=No, not very often; 2= Yes, some of the time; 3= Yes, most of the time; 4= not applicable |
| pcs_e10 | fq2.10 | Parenting confidence at 14 days Q10 | Ordinal | 0=No hardly ever; 1=No, not very often; 2= Yes, some of the time; 3= Yes, most of the time |
| pcs_e11 | fq2.11 | Parenting confidence at 14 days Q11 | Ordinal | 0=No hardly ever; 1=No, not very often; 2= Yes, some of the time; 3= Yes, most of the time |
| pcs_e12 | fq2.12 | Parenting confidence at 14 days Q12 | Ordinal | 3=No hardly ever; 2=No, not very often; 1= Yes, some of the time; 0= Yes, most of the time |
| pcs_e13 | fq2.13 | Parenting confidence at 14 days Q13 | Ordinal | 0=No hardly ever; 1=No, not very often; 2= Yes, some of the time; 3= Yes, most of the time |
| pcs_e14 | fq2.14 | Parenting confidence at 14 days Q14 | Ordinal | 0=No hardly ever; 1=No, not very often; 2= Yes, some of the time; 3= Yes, most of the time |
| pcs_e15 | fq2.15 | Parenting confidence at 14 days Q15 | Ordinal | 0=No hardly ever; 1=No, not very often; 2= Yes, some of the time; 3= Yes, most of the time |
| gc_end | fq3.1 | Global change at day 14 | Ordinal | 1=completely recovered, 2= much improved, 3= slightly improved, 4= No change, 5= Slightly worse, 6= Much worse, 7= vastly worse |
| ur_reported | fq3.2 | Concerns | Bi-nomial | 0=no, 1=yes |
| ur_typeX | fq3.3 | Concern type | Bi-nomial (7 variables) | 1- more distress 0= no, 1= yes 2- more crying 0= no, 1= yes 3- more unsettled 0= no, 1= yes 4- more vomiting 0= no, 1= yes 5- difficulties feeding 0= no, 1= yes 6- difficulties sleeping 0= no, 1= yes 7- other 0= no, 1= yes |
| ur_type7_txt | fq3.3.1 | Other concerns | Open text | String |
| other_careX | fq3.5 | Other care | Bi-nominal (8 variables) | 1- GP 0= no, 1= yes 2- A&E 0= no, 1= yes 3- unplanned hospital admission 0= no, 1= yes 4- other osteopath 0= no, 1= yes 5- paediatrician 0= no, 1= yes 6- pharmacist 0= no, 1= yes 7- lactation consultant or midwife 0= no, 1= yes 8- other 0= no, 1= yes |
| other_care8_txt | fq3.5.1 | Other care | Open text | String |
| pharmX | fq3.4 | Pharm & Supplements | Bi-nominal (7 variables) | 1- Prescribed medicine 0= no, 1= yes 2- Anti-gas drops 0= no, 1= yes 3- Herbal supplements 0= no, 1= yes 4- Probiotics 0= no, 1= yes 5- Non-cow or ant-allergenic formula milk 0= no, 1= yes 6- Omeprazole 0= no, 1= yes 7- Other 0= no, 1= yes |

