| d12 | diary | Crying time day 11 after treatment (mins) | Continuous | minutes |
| d13 | diary | Crying time day 12 after treatment (mins) | Continuous | minutes |
| d14 | diary | Crying time day 13 after treatment (mins) | Continuous | Minutes |

3. Serious Adverse Events (one line for each event)

Dataset name: sae.csv
Source: consultation information, open text from follow-up questionnaire
Format: csv

Details for data format: One line for each reported adverse event

| Variable | Source | Description | Type | Levels |
|----------|---------|--|-----------|---|
| id | SAE log | UID | Numerical | |
| Date | SAE log | Date of the event | Date | |
| sae_ser | SAE log | Level of seriousness | Nominal | 0=Non-serious adverse event 1=Unexpected hospital admission 2=Death 3=Irreversible morbidity |
| sae_rel | SAE log | Type of relationship with intervention | Nominal | 0=Not related, 1=Unlikely, 2=Possibly, 3=Probably, 4= Definitely |

4. Treatment (one line per treatment session)

Dataset name: treatment1.csv | treatment2.csv

Source: consultation information, follow-up questionnaire

Format: csv

Transformed data

- “treatment1” holds all the specific data from the test group (TTR). For the file to remain anonymous, the version that is sent to the statistician will have alternative IDs making impossible to match the data to individual data from the trial. The final archived dataset should contain true IDs.
- “treatment2” holds all the data on advice with ID data making it possible to link data to each participant and compare them between allocated groups.
- Text fields are uniquely for data cleaning purposes. This makes it possible to make sure each treatment is correctly categorised.

Details for data format “treatment1.csv”

| Variable | Source | Description | Type | Levels |
|-------------|---------------------------|---|-------------|-------------|
| id | Generated from study ID | Newly generated IDs to make it impossible for statistician to know which group is which | Numerical | |
| ttt_blt | os4.2 7.1 10.1 13.1 | BLT | Dichotomous | 0=no, 1=yes |
| ttt_btt_c | os4.3 7.2 10.2 13.2 | BTT(cranium) | Dichotomous | 0=no, 1=yes |
| ttt_btt_tpl | os4.4 ... | BTT(trunk, pelvis, limb) | Dichotomous | 0=no, 1=yes |
| ttt_btt_v | os4.5 | BTT(viscera) | Dichotomous | 0=no, 1=yes |
| ttt_btt_0 | os4.6 | BTT(other) | Dichotomous | 0=no, 1=yes |
| ttt_cff | os4.7 | Central fluid fluctuation (CFF) | Dichotomous | 0=no, 1=yes |

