This question asks about overall change in the infant's symptoms, from completely recovered to vastly worse. (Completely recovered, much improved, slightly improved, no change, slightly worse, much worse, vastly worse). These levels are coded numerically in an ordinal manner and are to be compared between groups using non-parametrical approaches.

Experience and satisfaction

Experience was measured using a 5-point likert scale from Very good, fairly good, neither good not bad, fairly poor and very poor.

Satisfaction was measured using a 5-point likert scale from Very satisfied, fairly satisfied, neither satisfied nor dissatisfied, fairly dissatisfied and very dissatisfied.

We also asked if the parent thought osteopathic care helped their baby using a yes, no or unsure response.

Unexpected and or Adverse events

We asked parents about additional care they may have administered to their infants and additional health care consultations they sought during the trial period as a proxy indicator of adverse events, and we also asked directly about any changes in symptoms that cause the parent concern. These included more distress, more crying, more unsettled, more vomiting, increased difficulty in feeding, sleeping and anything else (other).

Serious adverse events are reported by parents and managing osteopaths. These are assessed by the trial managing group and coded as for the reason for being a SAE and the estimated likelihood these are related to the treatment.

6. Randomisation

Block randomisation with variable block size of 4 and 6 generated by CastorEDC.

7. Sample size

From data collected during the pilot phase (n=13), we confirmed crying times as expected by Wolke et al. We estimate the average daily crying time over the two-week follow-up period to be of 120 minutes with a SD of 45 minutes. To detect a minimum of 30 minutes additional reduction in crying time between the intervention and control group with 90% power and a two-sided 5% significance level we would need 48 infants in each arm of the trial. If we allow for a 15% drop out we would need to randomise 112 infants, 66 in each arm of the trial. This sample size calculation is conservative because it disregards the fact that there are repeated measures in each infant and that the model will be corrected for the baseline crying time value. Thus, the actual power will be higher.

| Power | MCID (daily reduction in crying time in minutes) | | | |

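### The stated source of the serious adverse event file omits the parent's structured item on hospital admission, so an admission known only from that tick may be left out of the SAE count

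*SAP*

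**What the plan says.** Four parts of the SAP bear on this.

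- **SAE file (section 3, Serious Adverse Events).** The header reads "Source: consultation information, open text from follow-up questionnaire". The seriousness variable has the levels "0=Non-serious adverse event 1=Unexpected hospital admission 2=Death 3=Irreversible morbidity", and relatedness is coded "0=Not related, 1=Unlikely, 2=Possibly, 3=Probably, 4= Definitely". In the variable table, the source of all four variables is an SAE log.
- **Day-14 questionnaire (section 3, castor.csv).** The other-care question, fq3.5, is a set of eight yes/no items. One of them is "3- unplanned hospital admission 0= no, 1= yes".
- **Reporting and assessment (sections 5 and 8).** Section 5 says "Serious adverse events are reported by parents and managing osteopaths", and that the trial managing group then codes the reason for seriousness and the likely relation to treatment. It also treats extra care sought by parents as a proxy for adverse events. Section 8 says SAEs are monitored throughout the trial, and promises a total per group and a risk ratio.
- **Provisional tables (section 9).** Table 3 has a hospitalisation row under serious adverse events. Table 4 has "Unplanned hospital admission" under additional care.

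**The concern.** The SAP defines one kind of event as serious, asks parents about it directly, and then leaves the answer out of the stated source of the serious-event file. Parents are named as reporters of SAEs, but the only structured item in which they report an admission goes to a different dataset and a different table.

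What is at stake is the completeness of the safety report. An admission that stays outside the SAE log is missing from the Table 3 row, from the SAE total and from the risk ratio, and nobody codes its relation to treatment. A reader of the paper could also find an admission in Table 4 with no counterpart in Table 3 and no explanation. Serious events are likely to be few in a trial of 112 healthy infants, so one or two omissions could change the picture.

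**Working it through.** The SAP gives no figure for this point, so there is none to reproduce. The check is to follow one event, an unplanned admission, from collection to table.

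**Path A, the tick.** fq3.5 item 3 → other_care3 in castor.csv → additional-care block of Table 4.

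**Path B, the serious event.** Consultation information and follow-up open text (header), or SAE log (variable table) → sae_ser = 1 in sae.csv → hospitalisation row of Table 3, SAE total and risk ratio.

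Does anything stated in the SAP carry an event from A to B?

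1. *Open text.* The data dictionary has three follow-up open-text fields: ur_type7_txt, pharm7_txt and other_care8_txt. Each carries the number of an 'other' option, and none belongs to item 3. A parent who ticks the admission box need not write anything.
2. *Consultation information.* Section 2 describes this as the osteopath's report after each encounter. An admission after the last session has no later encounter in which to be recorded.
3. *Is the open-text limit deliberate?* The next dataset in section 3 (treatment) gives its source as consultation information and the follow-up questionnaire, with no such limit. The narrower wording for sae.csv therefore reads as a real restriction, though section 3 does not use its header lines strictly (see the objection).
4. *SAE log and direct reporting.* Sections 5 and 8 let parents report SAEs but do not name the channel. Neither says that a tick prompts a log entry or a query.
5. *Relatedness filter.* This cannot explain a difference between the tables, because the coding keeps events judged not related.

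So an admission known only from the tick counts 1 in Table 4 and 0 in Table 3.

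**Scale.** Section 7 randomises 112 infants, or 112 / 2 = 56 per arm. One infant is 1/56 = 1.8% of an arm. Section 7 also prints 66 per arm, which does not fit a total of 112 (2 × 66 = 132); on that figure one infant is 1/66 = 1.5%.

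**Illustration, assumed counts only.** Suppose 3 test and 1 control infants are admitted once each, and 2 of the test admissions are known only from the tick.

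| | Test | Control | Risk ratio |
|---|---|---|---|
| Table 4 (ticks) | 3/56 | 1/56 | 3.0 |
| Table 3 (SAE file) | 1/56 | 1/56 | 1.0 |

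Even 3 v 1 gives a two-sided Fisher p of about 0.62. The example shows how far a descriptive safety ratio can move. It does not show a change in any test result, and nothing in the SAP suggests that these counts are likely.

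**The case against.** The strongest reply is that the header line proves little. Every variable in sae.csv is sourced to an SAE log, and section 3 does not use its header lines as closed lists: the group.csv header names Castor and the main investigator, yet its variables also come from the diary, the data manager and the participant log. Sections 5 and 8 let parents report SAEs without tying that to a consultation or to free text, so a parent could report a late admission by another route. How an SAE log is filled and queried is often set out in the protocol, which is not at hand.

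Most of this stands, and it rules out two stronger readings. A reader might infer that every ticked admission is lost from the SAE file; the SAP does not support that, because the log and parental reporting may catch it. A reader might also infer that Tables 3 and 4 contradict each other unless their admission rows match. They need not match. sae.csv has one line per event, whereas other_care3 is one tick per participant, so two admissions of one infant are two events and one tick. An infant without a day-14 questionnaire can have a logged admission and no tick.

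What the reply does not remove is that this SAP itself states where its SAE dataset comes from, omits the item that records its own seriousness level 1, and names no step by which a tick reaches the log. Reporting the tick in Table 4 keeps it visible, but does not get it coded for seriousness and relatedness.

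**Conclusion.** The point holds as a gap in the stated data flow that permits an undercount of serious events. It does not show that an undercount will occur, and its size cannot be estimated from the SAP.

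It rests on three assumptions: that some admissions are known only from the tick, most plausibly those after the last session; that the parent does not report them by another route; and that no procedure outside the SAP compares the ticks with the log. If either of the last two fails, the loss shrinks or disappears.

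Severity is moderate. The SAE total, the risk ratio and the relatedness assessment could be affected; the primary outcome, its model and the sample size are not. It is still worth settling before unblinding, because deciding afterwards which ticks count as serious events would be open to question.

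**What to change.** 1. In section 3, add fq3.5 item 3 (other_care3) to the stated sources of sae.csv.
2. Before group identity is revealed under section 4, query every infant with other_care3 = 1 against the SAE log, and review every infant with other_care2 = 1 (A&E).
3. Have the trial managing group code seriousness and relatedness for any confirmed event not yet logged.
4. Do not require the two table rows to be equal. Add a footnote to Tables 3 and 4 that cross-references them, says that one counts events in the SAE file and the other counts participants with a tick on a completed day-14 questionnaire, and explains any remaining difference.

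The cost is a sentence or two in the SAP, a cross-check of two variables already collected, a few extra queries, and possibly a slightly higher reported SAE count.

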Corresponds to day-to-day reporting entry for crying time reported in minutes. Parents are asked to record their infants crying time to the nearest 5 minutes over 24 hours for 14 days. Each day starts at 6AM and finished the next day at the same time. Data is entered for each time slot separately. Each daily total is then compared to an independent day to day data entry (pseudo-double data entry). If daily sums do not match, the data is verified again, and errors are corrected. Data cleaning includes removing entries that would account for more than 24h of daily crying, reporting crying days from the day the first treatment was provided, transforming data when necessary (ex. 5 minutes time slots reported, graphical representation of crying time), replacing negative values or non-explicit string entries by missing values. Values are entered as minutes. Missing data is entered as blanks.

If some parents only report the daily total, these are to be recorded on a separate file (diary2.csv).

CastorEDC entries

Data is exported from the CastorEDC entry system from three separate forms:

1. *Baseline questionnaire (participant self report ; 24 questions)*
2. *Follow up questionnaire at 14 days post randomisation (participant self report, 27 questions)*
3. *Consultation information (osteopath reporting after each encounter)*

Data cleaning will be performed by the trial statistician consultation with the data manager

3. Datasets for data analysis

Six separate datasets are to be prepared.

1. *Merged data from Castor EDC (one line per participant)*

Dataset name: castor.csv

Source: CastrorEDC Baseline questionnaire (bq), follow-up questionnaire (fq) and consultation information (oq)

Format: csv

Details for data format

| Variable | Source | Description | Type | Levels |
|-------------|------------|--|-------------|--|
| id | bq, fq, oq | UID | Numerical | Nominal |
| pract | bq, oq | Practitioner | Numerical | Nominal |
| date_b | bq1.1 | Date of entry | Date | |
| date_end | fq1.1 | Date of last visit | Date | |
| parent_rel1 | bq1.2 | Relation to child for person answering 1 st questionnaire | Nominal | 1= mother, 2= father, 3=legal guardian, 4= other |
| parent_rel2 | fq1.2 | Relation to child for person answering 2 nd questionnaire | Nominal | 1= mother, 2= father, 3=legal guardian, 4= other |
| age | bq1.3 | Infant age (days) | Continuous | Days |
| bw | oq3.1 | Birth weight (Kg) | Continuous | Kg |

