| weight_b | oq3.2 | Weight current (Kg) | Continuous | Kg |
| weight_end | fq1.3 | Weight at end of follow-up | Continuous | Kg |
| ct_b | bq1.4/1.5 | Reported crying time prior 24h (min) | Continuous | Minutes |
| sibling | bq1.6 | Siblings | Ordinal | 0=0 , 1=1, 2=2, 3=3, 4=4, 5=5 or more |
| parent_age | bq1.7 | Age of parent (years) completing the questionnaire | Ordinal | 1= 18-20 years, 2=21-25 years, 3=26-30 years, 4=31-35 years, 5=36-40 years, 6= 41-45 years, 7= 46 – 50 years, 8= 50 years or older |
| parent_type | bq1.8 | Parenting type | Dichotomous | 1= co-parenting 2= parenting alone |
| gender | bq1.9 | Gender | Nominal | 0= female, 1= male, 2= other/undetermined/not willing to respond |
| expectation | bq1.10 | Expectation on treatment outcome | Nominal | 1 "Very well" 2 "Well" 3 "Unsure" 4 "Not very well" 5 "Not well" 6 "Missing" |
| pcs_b1 | bq2.1 | Parenting confidence at baseline Q1 | Ordinal | 0=No hardly ever; 1=No, not very often; 2= Yes, some of the time; 3= Yes, most of the time; 4= not applicable |
| pcs_b2 | bq2.2 | Parenting confidence at baseline Q2 | Ordinal | 0=No hardly ever; 1=No, not very often; 2= Yes, some of the time; 3= Yes, most of the time |
| pcs_b3 | bq2.3 | Parenting confidence at baseline Q3 | Ordinal | 0=No hardly ever; 1=No, not very often; 2= Yes, some of the time; 3= Yes, most of the time |
| pcs_b4 | bq2.4 | Parenting confidence at baseline Q4 | Ordinal | 0=No hardly ever; 1=No, not very often; 2= Yes, some of the time; 3= Yes, most of the time |
| pcs_b5 | bq2.5 | Parenting confidence at baseline Q5 | Ordinal | 0=No hardly ever; 1=No, not very often; 2= Yes, some of the time; 3= Yes, most of the time |
| pcs_b6 | bq2.6 | Parenting confidence at baseline Q6 | Ordinal | 0=No hardly ever; 1=No, not very often; 2= Yes, some of the time; 3= Yes, most of the time |
| pcs_b7 | bq2.7 | Parenting confidence at baseline Q7 | Ordinal | 0=No hardly ever; 1=No, not very often; 2= Yes, some of the time; 3= Yes, most of the time |
| pcs_b8 | bq2.8 | Parenting confidence at baseline Q8 | Ordinal | 0=No hardly ever; 1=No, not very often; 2= Yes, some of the time; 3= Yes, most of the time |
| pcs_b9 | bq2.9 | Parenting confidence at baseline Q9 | Ordinal | 0=No hardly ever; 1=No, not very often; 2= Yes, some of the time; 3= Yes, most of the time; 4= not applicable |

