Statistical blinding will be assured to generate summary variables and set the final analysis for between group differences. Once the final statistical coding is defined and validated by the TSC, the true group identity will be revealed and additional descriptive information on treatment will be provided.

- Coding allocation to random A, B to blind first step of statistical analysis
- Treatment description included in separate dataset to be coded with different IDS than main dataset.

5. Outcome measures

Primary Outcome measure

Crying time diary

The main outcome is daily crying time in minutes. This can be measured for crying times from the first day after treatment to the thirteenth day after treatment. Daily crying time is obtained by adding hourly reported crying times from 6AM to 5:59AM the next day. D-1 is computed from the hourly reported crying time on the day prior to the treatment if the entire day is completed. When incomplete, it is replaced by the parent reported 24h baseline crying time (castor.csv). Daily crying time is considered as missing if any of the time hour slots has missing values within the day.

The primary outcome is the between group average difference in crying time from day 1 after the treatment to day 13 after the treatment. Repeated measures random linear mixed effect adjusting for baseline crying time, expectations for treatment outcome and infant's age is used to estimate the between group difference.

If diaries only report the presence of crying during each hour slot, then each time slot is replaced by the corresponding median reported crying time for infants that were crying during that hour on that specific day of follow-up.

Secondary Outcome measure

Parent Confidence

Changes of parent confidence will be measured using the Parent Confidence Score at baseline and 14 day follow up. This score relies on 15 questions about parenting confidence with a likert scale of 4 choices (0 to 45 points). Changes over time will be measured at an individual level by adding the baseline value as a dependant variable in the mixed effect model. Movement of 6 points or more is to be considered as meaningful.

Global change

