Checking assumptions for primary outcome

a) Assumptions for repeated measures random linear mixed effect

The following assumptions for repeated measures random linear mixed effect need to be tested:

- The explanatory variables are related linearly to the response.
- The errors have constant variance.
- The errors are independent.
- The errors are normally distributed.

A graphical representation will plot the residuals against group allocation. This can indicate if the model fits the data appropriately. The residuals will also be plotted in the order of days after treatment to see any indications of visible trend over time. The residuals will be plotted against the fitted values to test whether there is any non-constant error variance. Finally, a histogram with a normal probability plot and Wilk-Shapiro test will be used to test the assumption of normality for crying-time distribution in each group.

If the distribution of crying time is not Gaussian, then it will be categorised, and the distribution of the response variable will be considered as ordinal, and the link function is logit. When the assumptions for distribution of the residuals are not met, transformation is to be used to make the analysis possible.

b) Testing and accounting for trends over time

Three methods are used to investigate trend over time:

- a. Visual and statistical assessment of trend over time is to be made using fractional polynomials in regression analysis separately for each group.
- b. Repeated measures random linear mixed model is to be used to test interactions between group allocation and days of follow-up. This makes it possible to assess that group differences are constant through time. Explanatory variables are group allocation, interaction between group allocation and number of days of follow-up, baseline crying time day before treatment, infant age at entry, treatment expectations. Linearity of response for the explanatory variable is tested as trends over time using mixed regression analysis.
- c. Day to day means in each group will be calculated using Delta-method linear prediction with fixed portion. Furthermore, linear trend over time will be tested in each group by modelling day to day residuals within the model.

Assumptions are to be verified on the linearity of the progression through time. Transformation is to be used if linearity is not met.

Secondary outcomes analysis

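### The baseline crying covariate mixes diary days with questionnaire values and carries no marker of source, which costs some precision that one model term can partly or largely recover

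*SAP*

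**What the plan says.** SAP section 5 (Crying time diary) gives the rule in two steps. First, "D-1 is computed from the hourly reported crying time on the day prior to the treatment if the entire day is completed". Second, "When incomplete, it is replaced by the parent reported 24h baseline crying time (castor.csv". On what counts as incomplete, the same section says "Daily crying time is considered as missing if any of the time hour slots has missing values within the day", so one blank hour is enough to trigger the switch.

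The two sources are collected differently. For the diary, section 2 says "Parents are asked to record their infants crying time to the nearest 5 minutes over 24 hours for 14 days", and each day runs from 6AM. The fallback is `ct_b` in castor.csv, taken from baseline-questionnaire items 1.4/1.5 and described as "Reported crying time prior 24h (min".

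Section 8 (Primary outcome analysis) lists baseline crying as one continuous explanatory variable without naming the dataset variable. The section on trends over time is more specific: its covariates include "baseline crying time day before treatment, infant age at entry, treatment expectations", which points to D-1. Neither model has a term for source, and none of the analyses listed in section 8 uses a single baseline source. The analysis without imputed medians deals with hourly slots where crying was noted without a duration, which is a different matter.

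**The concern.** A log kept hour by hour and a retrospective 24-hour report need not agree on average, and need not predict later crying equally well. They may also cover different 24-hour windows. When both feed one column with one slope, a systematic gap between them acts as noise in the covariate. Adjustment then removes less residual variance than it could.

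What is at stake is precision, and how one table row reads. Table 2 has a row for the day before treatment above the treatment and follow-up days. If D-1 fills that row, questionnaire values will sit in a column of diary values with nothing to distinguish them.

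**Working it through.** **Plan's own figure.** Inputs from SAP section 7: difference 30 min, SD 45 min, two-sided 5%, power 90%.

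- n per arm = 2 × 45² × (1.960 + 1.282)² / 30² = 47.3, rounded up to 48. This matches the SAP.
- Unadjusted SE with 48 per arm = 45 × √(2/48) = 9.19 min, power 90.4%.

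This calculation takes no credit for baseline adjustment, so a weaker covariate cannot make 48 too small.

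**Cost of mixing, by formula.** Assumptions that are not in the SAP: the baseline SD is 45 min within each source (the SAP gives 45 for the two-week average, not for one day); both sources correlate 0.5 with follow-up crying; they differ by a constant gap b; a share f of values comes from the questionnaire.

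- Variance added to the covariate: f(1 − f)b², on top of 45² = 2025.
- Reduced correlation: r′ = 0.5 × √(2025 / (2025 + f(1 − f)b²)).
- Variance of the group difference relative to one source: (1 − r′²) / 0.75.

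For b = 60 and f = 0.1, the added variance is 0.09 × 3600 = 324, r′ = 0.464 and the ratio is 1.05. For f = 0.5, it is 0.25 × 3600 = 900, r′ = 0.416 and the ratio is 1.10.

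| Gap b (min) | f = 0.1 | f = 0.2 | f = 0.5 |
|---|---|---|---|
| 30 | 1.01 | 1.02 | 1.03 |
| 60 | 1.05 | 1.07 | 1.10 |
| 120 | 1.13 | 1.18 | 1.21 |

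The f = 0.5 column is the worst case, because f(1 − f) peaks there. With one source the SE is 9.19 × √0.75 = 7.96 min (power 96.5%). At b = 60 and f = 0.5 it is 7.96 × √1.10 ≈ 8.35 min (power about 95%). At b = 120 and f = 0.5 it is 8.76 min (power 92.8%). All stay above 90.4%.

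**Simulation, constant gap.** With 3,000 trials of 96 infants, b = 60 and f = 0.5, the SE was 7.96 with one source, 8.40 mixed and 7.98 mixed with a source indicator. The indicator recovers nearly all the loss here because the sources differ only by a constant.

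**Simulation, less predictive questionnaire.** Different assumptions: baseline SD 60 min, diary correlation 0.6, questionnaire correlation 0.3, gap 60 min, 30% replaced.

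| Baseline covariate | Residual SD (min) | Power at 48 per arm |
|---|---|---|
| Diary for all | 36.0 | 98.3% |
| Mixed, as planned | 39.8 | 95.8% |
| Mixed plus source indicator | 38.7 | 96.7% |
| Mixed plus indicator and its interaction with baseline | 38.2 | 97.0% |
| Questionnaire for all | 42.9 | 92.8% |

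Here the indicator recovers 1.1 of the 3.8 min lost. Over all scenarios run (questionnaire correlation 0.3 or 0.6, gap 0 to 120 min, 10% to 50% replaced), the mixed covariate gave power from 93.1% to 98.3%.

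**Validity.** In 20,000 simulated trials per scenario, with source unrelated to outcome, the mean estimate at 30% replaced and a 60-min gap was −0.1 min under no effect and −30.1 min under a true −30. The rejection rate under no effect was 4.9%, both there and at 50% replaced with a 120-min gap.

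**The case against.** The strongest reply is that preferring the diary day and falling back on a 24-hour report is a sensible prespecified rule. It uses the same instrument as the outcome where it can, and it keeps infants in the model. That stands, and the rule should stay.

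It also stands that randomisation protects the comparison. A reader might infer that mixing sources biases the treatment effect, since careful and less careful diary keepers may differ in later reported crying. Provided the baseline is recorded before allocation can influence it, that is at most an unmodelled prognostic factor. If the questionnaire share differed by 10 percentage points between arms by chance, the estimate would move by about 1.6 to 4.0 min for gaps of 60 to 120 min. The confidence interval already allows for chance movement of that kind. A reader might also infer that the trial loses power the plan relied on. Section 7 says only that actual power will exceed the calculated figure, and in every scenario above it does.

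Three further inferences are too thin to use:

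- *The questionnaire measures something wider than crying.* This rests on the Table 1 label "Excessive crying, distress or unsettlement prior 24h; mean (SD". The data dictionary describes `ct_b` as crying time, and the item wording is not shown. Two item numbers are cited, so calling it a single question is not supported either.
- *The switch will be frequent.* Section 2 describes 14 diary days, while diary2.csv spans 15 dates. This does not give the replacement share. If most diaries lacked the day before treatment, nearly everyone would have `ct_b` and there would be little mixing.
- *The entry threshold shows the size of the gap.* More than 3 hours a day at entry against a planning mean of 120 min in follow-up compares two times in a self-limiting condition, not two instruments.

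The planned work on missing data and the adjustment for baseline imbalance come near this point, but neither separates the baseline value by source.

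**Conclusion.** The point holds as a modest matter of precision. The planned covariate combines two measures without a marker, and the variance of the group difference rises by about 5% to 10% for 10% to 50% replaced, given SD 45 min, correlation 0.5 and a 60-min gap. The gap, the share replaced and the correlations are all assumptions. A smaller gap or a larger single-day SD would shrink the loss, and a larger gap would raise it (up to 21% at 120 min with half replaced). The SAP does not support a claim of bias, of inflated type I error or of too small a sample. The change is worth making because it is cheap and keeps every infant in the analysis.

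**What to change.** - In SAP section 8, state that the baseline covariate in the primary model is D-1 as defined in section 5, with its fallback. Say also how a day-before-treatment total held only in diary2.csv is classed, since the rule mentions hourly entries alone.
- Add one prespecified binary term for the source of that value (diary or questionnaire) to the primary model.
- Report the number of values from each source by arm.
- Fill the day-before-treatment row of Table 2 from complete diary days only, with its own n.
- Use `ct_b` for all infants at most as a sensitivity analysis. If it predicts later crying less well than the diary day, it does worse than the planned mixture (42.9 against 39.8 min in the second simulation). If it predicts equally well, it would do as well as the diary.

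The cost is a few lines of SAP text, a flag derived from data already planned for collection, and 1 degree of freedom.
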